11.1.2 Analysis of secondary endpoints

11.1.2.1 Safety

Patients will be assessed for toxicities at each clinical evaluation. Toxicities will be graded according to CTCAE v.5.0 standardized grading scales. The incidence of

grade 3-5 toxicities will be reported. Patients will be assessed for toxicity as long as they are taking nivolumab, and patients will continue to be followed if treatment is discontinued for toxicity until the toxicities improve to grade 1 or resolve.

Toxicities will be reported as a tabulated table by type and grade.

11.1.2.2. PSA progression-free survival (PSA-PFS)

A standard definition of PSA progression per PCWG3 will be used. PSA PFS will be defined as an increase in 25% over a nadir value, confirmed by a follow-up PSA at least 4 weeks apart. If patients are removed from study prior to PSA progression, then they will be censored at that time.

We will use the Kaplan-Meier method to summarize the PSA PFS.

11.1.2.3. Undetectable PSA

Undetectable PSA will be defined as the proportion of patients that achieve a PSA <0.1 ng/ml last \geq 12 weeks.

11.1.2.4 Metastasis-free survival

Metastasis-free survival will be defined as the time from the first dose of nivolumab until the development of radiographic metastatic disease as determined by CT imaging and/or bone scan. If a patient is removed from the study prior to the development of metastatic disease, they will be censored at that time.

We will use the Kaplan-Meier method to summarize the metastasis-free survival.

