Rationale	
Disease Background: MMR-deficient cancers of any histologic type appear to be very sensitive to PD-1 blockade with pembrolizumab, and similar data are also beginning to emerge for nivolumab and other immune checkpoint inhibitors. Among the MMR-deficient cancers, the best antitumor responses are often associated with high microsatellite instability (MSI-H status), higher tumor mutational burden (TMB), and higher predicted neoantigen load. Prevalence estimates of MMR deficiency across solid tumor types range from 1% to 20% depending on the type of malignancy. In prostate cancer, 1-3% of unselected cases harbor MMR deficiency and/or microsatellite instability.
 
For men who previously received definitive treatment for prostate cancer and subsequently develop detectable prostate specific antigen (PSA) levels, the clinical state is known as biochemically recurrent prostate cancer. The current standard of care treatment for patients with biochemically recurrent prostate cancer is either surveillance or androgen deprivation therapy (ADT). ADT has not been shown to provide a survival benefit in this setting, and the decision to initiate ADT will depend on patient preference and perceived risks of the disease. A non-hormonal therapy such as nivolumab would provide an alternative to ADT in patients with biomarker selected (i.e. dMMR, MSI-H, high TMB, or CDK12-altered) biochemically recurrent prostate cancer.

Objectives	
Primary: To estimate the PSA₅₀ response rate, defined as a $\geq 50\%$ decline in PSA from baseline, confirmed with a second measurement at least 4 weeks apart (PCWG3).
 
Secondary:
 
 • To estimate the median PSA progression-free survival (PSA-PFS)(PCWG3). • To estimate the the proportion of patients that achieve an undetectable PSA (i.e. PSA <0.1) lasting ≥ 12 weeks • To estimate median metastasis-free survival (PCWG3) • To estimate median time to initiation of next systemic therapy • To determine the safety and tolerability of nivolumab in the biochemical recurrent prostate cancer population. 
Correlatives/Tertiary:

Criteria for
evaluation

Primary Endpoint

- PSA₅₀ response rate, defined as a $\geq 50\%$ decline in PSA from baseline, confirmed with a second measurement at least 4 weeks later (PCWG3).

Secondary Endpoints

- Safety/Tolerability, defined as incidence of CTCAE v.5.0 Grade ≥ 3 toxicities experienced by patients on the trial.

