3.2 Expected Enrollment

A total of 15 patients will be included in this study. The first patients are expected to be enrolled in Q3 2019. Accrual is expected to be completed in 12 months once the protocol has been approved by the IRB at each participating institution. After the last patient is enrolled, we expect approximately 6 months additional followup.

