5. TREATMENT/INTERVENTION PLAN

The following assessments and procedures will occur during the study. A schedule of assessments is provided in Table 1.

Nivolumab in Biochemically Recurrent dMMR Prostate Cancer
Johns Hopkins

Table 1 Study Calendar

	Pre-study	Study Period					Off study follow-up
		On Treatment Assessments (Every 28 days)				End of Treatment Visit	
	Day -28 to -1 ^a	C ₁ D ₁ (±5 d)	C ₂ D ₁ (±5 d)	C ₃ D ₁ (±5 d)	C _N D ₁ (±5 d)	28 days after last dose (±5 d)	Every 28 days ^d & 100 days after last dose (±5 d)
Informed consent	X						
Demographics	X						
Complete Medical history	X						
EKG	X						
Height	X ^g						
Weight	X ^g	X	X	X	X	X	X
Nivolumab		X	X	X	X		
Focused Medical history	X	X	X	X	X	X	X
Concomitant meds	X	X	X	X	X	X	
ECOG Performance status	X	X	X	X	X	X	X
Physical exam	X ^g	X ^g	X ^g	X ^g	X ^g	X ^g	X ^g
Vital signs (P, BP, RR, T)	X ^g	X ^g	X ^g	X ^g	X ^g	X ^g	X ^g
Toxicity assessment		X	X	X	X	X	X
CBC w/ diff ^e	X	X ^f	X	X	X	X	
CMP ^e	X	X ^f	X	X	X	X	
PSA ^e	X	X ^f	X	X	X	X	
Serum Testosterone ^e	X	X ^f	X	X	X	X	
Serum Amylase/Lipase/CK/TSH with Reflex T3/T4 ^e	X	X ^f	X	X	X	X	
Hepatitis B/C; PTT, PT/INR, Urinalysis	X						
Radiologic tests ^b	X				X ^b	X ^b	
Archival Tissue/DNA/RNA studies	X						
Plasma for PBLs/Phipseq		X ^c	X ^c		X ^c	X ^c	
Adverse events			X	X	X	X	X ^d

Abbreviations: CBC, complete blood count; CT, computerized tomography; MRI, magnetic resonance imaging; PSA, prostate-specific antigen; PBLs, peripheral blood leukocytes; CK, creatine kinase; TSH, thyroid stimulating hormone

^a Informed consent must be obtained within 4 weeks and radiologic assessments should be obtained within 8 weeks of study start date.

Nivolumab in Biochemically Recurrent dMMR Prostate Cancer

Johns Hopkins

- ^b Radiographic evaluations (CT C/A/P and NM Bone Scan every 6 months while enrolled in the study). They are needed within 8 weeks of screening; if previously performed then they are to be performed at screening. CT C/A/P and NM Bone Scan are to be performed at the end of treatment visit if they have not been performed within the prior month. If PSA becomes undetectable, CT C/A/P can be obtained in a timeframe at PI discretion
- ^c Plasma for PBLs/PHipSeq will be drawn before treatment administration at C1D1, C2D1, C4D1, and at progression (EOT).

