- ^d Subjects will be followed after completion of nivolumab therapy monthly until toxicities resolve to grade 0-1 if they withdrew because of AEs. Otherwise, subjects will be followed at 100 days after last dose for AE reassessment. This 100 day visit may take place via telephone.
- ^e All labs should be drawn before treatment administration.
- ^f Labs do not need to be repeated if done within 7 days of screening.
- ^g Physical exam (including vital signs/height/weight) may be missed if not clinically-indicated, or in the event of a telemedicine visit. In order to minimize the need for research-only in-person visits, telemedicine visits may be substituted for in-person clinical trial visits or portions of clinical trial visits where determined to be appropriate and where determined by the investigator not to increase the participants risks. Prior to initiating telemedicine for study visits the study team will explain to the participant, what a telemedicine visit entails and confirm that the study participant is in agreement and able to proceed with this method. Telemedicine acknowledgement will be obtained in accordance with the Guidance for Use of Telemedicine in Research. In the event telemedicine is not deemed feasible, the study visit will proceed as an in-person visit. Telemedicine visits will be conducted using HIPAA compliant method approved by the Health System and within licensing restrictions.

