7.8 Removal of Subjects from the Study, Therapy Assessment

7.8.1 Subject withdrawal

Single subject termination is by definition when the patient is withdrawn or when the patient has died. The study termination page in the eCRF must be completed.

The Investigator also has the right to withdraw subjects from the study in the event of:

- Occurrence of an exclusion criterion, which is clinically relevant and affects the subject's safety, and discontinuation is considered necessary by the Investigator and/or the Sponsor.
- Therapeutic failure requiring urgent additional medication (if applicable)
- Occurrence of AEs, if discontinuation of study medication is considered necessary by the Investigator and/or subject (if applicable).
- Intake of non-permitted concomitant medication as defined in Appendix A where the predefined consequence is withdrawal from the study.
- Progression of disease (subjects will only come off study after meeting PCWG3 criteria for radiographic progression or clinical progression as determined by the treating physician).
- Lack of subject compliance.
- Protocol violation.

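### Metastasis-free survival omits death and censors at study removal, next therapy is not collected beyond day 100, and 6 to 18 months of follow-up is too short for the promised median if it is long

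*Combined protocol and SAP*

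**What the plan says.** - **Event and censoring.** The synopsis and sections 9.1.2.4 and 11.1.2.4 all define MFS as time from first dose to radiographic metastasis on CT and/or bone scan. Death is not mentioned. Section 11.1.2.4 continues: "If a patient is removed from the study prior to the development of metastatic disease, they will be censored at that time".
- **Death.** Section 7.8.1: "Single subject termination is by definition when the patient is withdrawn or when the patient has died".
- **Removal.** Section 7.8.1 lists therapeutic failure and progression among the reasons for withdrawal, and limits removal for progression to radiographic or clinical progression. Section 9.1.2.2 lets men stay on study beyond PSA progression. The synopsis, under secondary endpoints, lets them stay only until PSA doubles from baseline.
- **Scans.** Table 1 footnote b asks for scans every 6 months while enrolled; section 5.2.2 says every 6 cycles from C7D1. Footnote b and section 5.3 add a scan at end of treatment or study exit if none was done in the prior month. The off-study column of Table 1 has no radiology, PSA or concomitant-medication entry.
- **After treatment.** Men who withdrew for adverse events are followed monthly until these settle. For the rest, Table 1 footnote d says: "Otherwise, subjects will be followed at 100 days after last dose for AE reassessment". Focused medical history is marked in the off-study column. The heading of section 5.4 names survival status, but no schedule or duration follows.
- **Time to next therapy.** Section 11.1.2.5 censors at last follow-up men who withdraw consent or are lost. It has no rule for men whose planned contact simply ends.
- **What is promised.** The synopsis objectives include median MFS and "To estimate median time to initiation of next systemic therapy". Section 2.2 lists neither endpoint, and section 11 says only that Kaplan-Meier will summarise them.
- **Horizon.** Section 3.2: "A total of 15 patients will be included in this study"; accrual takes 12 months; "After the last patient is enrolled, we expect approximately 6 months additional followup".

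**The concern.** An endpoint with survival in its name should not treat a death as a censored observation.

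Kaplan-Meier also assumes that men censored at a given time have the same later risk as those who remain. A man removed for clinical progression or therapeutic failure probably has a higher risk. Censoring him drops the metastases that would follow, and the curve stays too high. With no comparator arm, nothing in the trial would expose this.

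Next systemic therapy usually starts after nivolumab stops, which is when planned data collection ends. Finally, a median reported as not reached after short follow-up can be mistaken for activity.

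**Working it through.** **The plan's own figures.** The only numerical justification is the table of Wilson intervals for the PSA50 rate with n = 15. All ten rows reproduce (3/15 gives 7.0–45.2%; 12/15 gives 54.8–93.0%). No expected median, event count or precision is given for MFS or time to next therapy, so the true medians, removal times and correlations below are assumptions shown as ranges.

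**Follow-up.** The first man has 12 + 6 = 18 months and the last has 6. With uniform accrual the mean is 12 months, or 15 × 12/12 = 15 patient-years.

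**Deaths.** At an assumed 1% to 5% per year, 15 × 0.01 = 0.15 to 15 × 0.05 = 0.75 deaths are expected.

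**Chance that the MFS median is reached.** Simulation of 2,000 trials per cell: n = 15, uniform 12-month accrual, cut-off 6 months after the last entry, exponential event times, metastasis detected at the next 168-day scan or at the exit scan. Reached means that the Kaplan-Meier curve falls to 0.5 or below. The simulation error near 33% is √(0.33 × 0.67/2000), about 1 point.

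| True median MFS (months) | 12 | 18 | 24 | 36 | 60 |
|---|---|---|---|---|---|
| No early removal | 59% | 33% | 21% | 11% | 6% |
| Removal median 6 months, unrelated to risk | 60% | 37% | 27% | 18% | 9% |
| Removal median 6 months, correlation 0.6 with metastasis time | 28% | 12% | 7% | 3% | 1% |
| All men scanned to the same cut-off | 59% | 32% | 22% | 10% | 7% |

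Without removal, mean events are 6.0, 4.5, 3.5, 2.4 and 1.5. The first and last rows agree within simulation error. So the low chance in the first row comes from the horizon and not from the censoring rule, although removal related to risk would lower it further. Every scan is assumed to be on schedule. Footnote b relaxes this for responders ("If PSA becomes undetectable, CT C/A/P can be obtained in a timeframe at PI discretion"), which is not modelled.

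**Value of the exit scan.** With unrelated removal at a median of 9 months and true medians of 12, 24, 36 and 60 months, expected events are about 3.5, 2.0, 1.4 and 0.9 without the exit scan, and about 4.4, 2.5, 1.7 and 1.1 with it.

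**Bias from censoring at removal.** The true 12-month metastasis-free rate is 0.5^(12/m) for median m; for m = 24 it is 0.5^0.5 = 0.707. Large-sample Kaplan-Meier values at 12 months, with removal at a median of 6 months and any metastasis before removal counted:

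| True median (months) | True rate | Correlation 0 | 0.3 | 0.6 |
|---|---|---|---|---|
| 18 | 0.630 | 0.633 | 0.706 | 0.798 |
| 24 | 0.707 | 0.708 | 0.778 | 0.862 |
| 36 | 0.794 | 0.795 | 0.852 | 0.921 |

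For m = 24 the excess is 0.778 − 0.707 = 0.071 at correlation 0.3 and 0.862 − 0.707 = 0.155 at 0.6.

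**Time to next therapy.** Event time = time to end of treatment + gap. Chance that the median is reached:

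| End of treatment, median (months) | Gap, median (months) | Seen to 100 days | Seen to cut-off |
|---|---|---|---|
| 4 | 1 | 99% | 100% |
| 6 | 1 | 94% | 97% |
| 6 | 3 | 53% | 86% |
| 6 | 6 | 22% | 60% |
| 12 | 3 | 20% | 44% |

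The 100-day limit can also push the estimate up. With medians of 4 and 3 months the true median is 8.4 months; the typical Kaplan-Meier median is 10.2 with 100-day capture and 8.5 with follow-up to cut-off.

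**The case against.** The strongest reply is that the documents limit the damage, and most of it stands.

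- An exit scan is planned, so metastasis visible when a man leaves is an event. Radiographic progression is likewise an event (section 9.4.1).
- If removal is unrelated to metastasis risk, the bias is nil. How often removal precedes metastasis turns on which removal passage governs.
- Few deaths are expected, and the heading of section 5.4 names survival status, so vital status is partly planned.
- Off-study focused medical history could pick up new treatment until day 100. Section 11.1.2.5 does not censor time to next therapy at study removal.
- Both endpoints are secondary and descriptive, and the medians appear only in the synopsis.

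This narrows the point but leaves three gaps: how death is handled in MFS, what is collected after exit, and what happens to a man without the event when contact ends. Clinical progression and therapeutic failure are listed reasons for withdrawal, so removal wholly unrelated to risk is the less plausible case.

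**Conclusion.** The point holds at moderate severity. As written, MFS censors deaths and censors men at removal for reasons plausibly tied to their risk. If the tie exists, the 12-month rate is overstated by about 7 to 16 points (true median 24 months, removal median 6 months, correlation 0.3 to 0.6, all assumed). Scheduled scanning stops at exit, and no procedure records next therapy after day 100.

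Separately, the promised median MFS is unlikely to be reached if the true median is about 18 months or more. The documents give no expected value.

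A reader might infer more than this:

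- *That the censoring and death rules are why the median cannot be estimated.* The 33%, 21% and 11% figures contain neither removals nor deaths.
- *That MFS is necessarily biased.* That needs removal related to risk, and the passages on removal conflict.
- *That median time to next therapy will usually not be reached.* With a gap of about 1 month and treatment ending at a median of 4 to 6 months, it is reached in 94% to 99% of simulated trials.
- *That omitting death moves the result much.* Fewer than one death is expected at the assumed rates, so this is an error of definition.
- *That the trial's main conclusion is at risk.* The PSA50 primary endpoint is unaffected, and no effect on PSA-PFS has been shown.

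**What to change.** 1. Define the MFS event as radiographic metastasis or death from any cause. Alternatively, rename the endpoint time to metastasis and treat death as a competing event.
2. Do not censor MFS at treatment or study removal, except on withdrawal of consent. Collect metastasis on standard-of-care imaging, start of next systemic therapy and vital status by phone or chart at day 100, then about every 3 months to the study cut-off. Censor MFS at the last adequate scan. Censor time to next therapy at last contact for every man without the event.
3. In the objectives and section 11, report Kaplan-Meier estimates with confidence intervals at 6 and 12 months, and the median only if reached. Step 2 alone will not secure the MFS median at the planned cut-off.
4. Reconcile the synopsis with sections 7.8.1 and 9.1.2.2 on when a man leaves the study.

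The cost is one form and a few contacts for 15 men, with no extra study scans. MFS may look shorter. Standard-of-care imaging after exit will be less regular than study scans, and MFS will then include metastases that appear after next therapy has begun; the report should say so.

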11.1.2.5 Time to initiation of next systemic therapy

Time to initiation of next systemic therapy will be defined as the time from the first dose of nivolumab until the next systemic therapy is initiated. For patients that withdraw consent or are lost to follow-up, they will be censored at the time of last follow-up.

Will use the Kaplan-Meier method to summarize the time to initiation of next systemic therapy.

11.1.3 Analysis of exploratory endpoints

11.1.3.1 PD-1, PD-L1, CD4, CD8, FOXP3, MSH2, MSH6, MLH1, PSM2, CDK12 protein levels:

Archival tumor specimens including prostatectomy or needle biopsy of primary tumor, will be analyzed. IHC staining for PD-1 and PD-L1 will be performed and scored as <1%, 1-5%, 5-10%, >10% and the results will be associated with responses for both proteins, separately, using descriptive statistics and Fisher's Exact Tests. IHC will be used to quantify the CD4, CD8, and FOXP3 levels. Using analytical microscopy, the lead pathologist, [name] can quantify the number of T cells per surface area of tumor analyzed. The median number of CD4+ and CD8+ intratumor lymphocytes will be compared in PSA₅₀ responders versus non-responders using a T-test. We will also correlate CD4+ and CD8+ lymphocyte tumor infiltration in patients that obtain an undetectable PSA versus those with

progressive disease as best response. Lastly, we will correlate response to nivolumab with MMR and CDK12 mutational status.

11.1.3.2 Interrogate for tumor-associated neoantigens (TAAs):

Whole-exome and RNA sequencing will be performed on archival tissue. Exome data will be applied in a neoantigen prediction pipeline that evaluates antigen processing, MHC binding and gene expression to generate neoantigens specific to the patient's HLA haplotype. TCR sequencing will also be performed on intratumor T cells as well as T cells in the peripheral blood. T cells will be collected prior to therapy, after 1 and 3 cycles of nivolumab and progression. Truncal neoantigens will be identified by correcting for tumor purity and ploidy. Putative neoantigens will then be used to generate peptides and stimulate autologous T cells.

11.1.3.3 Interrogate for auto antigens mimicking TAAs:

Peripheral blood samples will be processed using Phase ImmunoPrecipitation Sequencing (PhIP-seq). A human 90-mer peptidome library which encodes 259,346 peptides that tile the complete human proteome has been developed. The oligonucleotide library was printed on a releasable DNA microarray, and cloned into a T7 phage display system. The phage library is mixed with samples containing antibodies, and antibody-bound phage are captured on protein A/G coated magnetic beads. DNA from the enriched phage population is recovered and inserts are PCR amplified with sequencing adapters and sample-specific barcodes for deep DNA sequencing analysis.

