- PSA progression-free survival (PSA-PFS), defined as a time from initiation on nivolumab therapy until PSA increase of 25%, confirmed with another measurement at least 4 weeks later (PCWG3). Patients will be allowed to stay on study until PSA increases 100% (i.e. doubles) from baseline value.
- Metastasis-free survival (PCWG3)
- Undetectable PSA: Defined as a PSA level <0.1 lasting ≥ 12 weeks
- Time to initiation of next systemic therapy

Exploratory Endpoints

- To associate PSA₅₀ response to nivolumab with CD4, CD8, FOXP3, PD-1, PD-L1 levels, MMR and CDK12 mutational status by IHC in archival tumor tissue.
- To associate clinical responses to nivolumab with the expansion of anti-tumor peripheral T cell clones.
- To associate clinical responses to nivolumab with generation of tumor associated antigens as determined by PhIP-seq testing.
- To investigate primary and acquired resistance to PD-1 inhibitor therapy in these biomarker-selected patients (JAK1/2 mutations, B2M expression)

Exploratory Analyses

PD-1, PD-L1, FOXP3, CD4, CD8, MSH2, MSH6, MLH1, PSM2, CDK12 protein levels:

Archival tumor specimens including prostatectomy or needle biopsy of primary tumor, will be analyzed. IHC staining for PD-1 and PD-L1 will be performed and scored as $<1\%$, $1-5\%$, $5-10\%$, $>10\%$ and the results will be associated with responses for both proteins, separately, using descriptive statistics and Fisher's Exact Tests. IHC will be used to quantify the CD4, CD8, and FOXP3 levels. Using analytical microscopy, [name] can quantify the number of T cells per surface area of tumor analyzed. The median number of CD4+ and CD8+ intratumor lymphocytes will be compared in PSA₅₀ responders versus non-responders using a T-test. We will also correlate CD4+ and CD8+ lymphocyte tumor infiltration in patients that obtain an undetectable PSA versus those with progressive disease as best response. Lastly, we will correlate response to nivolumab with MMR and CDK12 mutational status.

Interrogate for tumor-associated neoantigens (TAAs) and mutation-associated neoantigens (MANAs):

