Biochemically-recurrent prostate cancer (*i.e.* manifesting by a rising PSA level after local therapy), represents an ideal space for deploying immunotherapy in this disease. These patients have not yet received androgen deprivation therapies (*i.e.* are non-castrate), and do not have radiographic evidence of metastases, yet are incurable and will eventually develop both metastatic and castrate-resistant prostate cancer. This population also represents an ideal setting to study a non-castrating systemic therapy, which will not be influenced by androgen levels or their suppression. To maximize the chance for success, we propose to focus on the dMMR/MSI-H patient population for treatment with nivolumab (without ADT).

While the overall prevalence of dMMR/MSI-H prostate cancer is 1-3%, our group has shown that there may be enrichment in certain histologic subtypes. For example, the prevalence of dMMR/MSI-H prostate cancer increases to 8-15% among patients with primary Gleason pattern 5 (*i.e.* Gleason scores 5+5 or 5+4), those with intraductal or ductal histology (as opposed to typical acinar histology), and those with neuroendocrine small cell prostate cancer (unpublished data). By targeting our prescreening efforts on these histologic subtypes, it becomes much more feasible to contemplate a study specifically in dMMR prostate cancer.

We hypothesize that nivolumab monotherapy (without ADT) will have clinical activity in a significant proportion of dMMR/MSI-H prostate cancers with a PSA recurrence following local therapy. Further, we hypothesize that the most favorable responses to nivolumab will be seen in patients with high tumoral lymphocytic infiltrate, positive PD-1 and PD-L1 expression, and high tumor mutational burden (TMB).

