9.3 Response Criteria for Primary and Secondary Endpoints

9.3.1 PSA

For each patient, use a waterfall plot to report the percent change in PSA from baseline to 12 weeks (or earlier for those who discontinue therapy) and the maximum decline in PSA that occurs at any point after treatment. We will also report the proportion of patients to achieve a 50% or greater decrease in PSA from baseline (i.e. PSA₅₀ response rate).

9.4 Criteria for Progressive Disease.

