11. STATISTICAL CONSIDERATIONS

The sample size of 15 patients will provide a preliminary evaluation of clinical activity based on PSA response. Two-sided 95% Wilson confidence interval for various scenarios of PSA₅₀ response rate is presented in the table below:

Number of PSA ₅₀ response	Observed PSA ₅₀ response rate	95% confidence interval
3	20%	7.0 – 45.2%
4	26.7%	10.9 – 52.0%
5	33.3%	15.2 – 58.3%
6	40%	19.8 – 64.3%
7	46.7%	24.8 – 69.9%
8	53.3%	30.1 – 75.2%
9	60%	35.7 – 80.2%
10	66.7%	41.7 – 84.8%
11	73.3%	48.0 – 89.1%
12	80%	54.8 – 93.0%

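### PD-1 and PD-L1 are scored in four ordered classes but tested against PSA50 response with an order-blind Fisher test; an exact trend test would use the order at almost no cost

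*Combined protocol and SAP*

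**What the plan says.** Section 11.1.3.1, repeated in the synopsis under Exploratory Analyses, sets out these steps:

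- **PD-1 and PD-L1.** Archival tissue is scored as below 1%, 1-5%, 5-10% or above 10%, and "the results will be associated with responses for both proteins, separately, using descriptive statistics and Fisher's Exact Tests". This sentence does not define response. The synopsis exploratory endpoints and section 2.3 show that PSA50 is meant.
- **CD4+ and CD8+.** Counts of "intratumor lymphocytes will be compared in PSA₅₀ responders versus non-responders using a T-test".
- **A further CD4+/CD8+ comparison**, "in patients that obtain an undetectable PSA versus those with progressive disease as best response". No test is named.

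Section 1.3.1 hypothesises that "the most favorable responses to nivolumab will be seen in patients with high tumoral lymphocytic infiltrate, positive PD-1 and PD-L1 expression". Section 9.3.1 already derives, for each man, the percent PSA change from baseline to 12 weeks (or earlier if therapy stops) and "the maximum decline in PSA that occurs at any point after treatment", both for waterfall plots.

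No trend test is planned, and no biomarker analysis uses percent PSA change. The documents give no alpha, effect size, expected class distribution or power for these tests. Section 11 says only: "The sample size of 15 patients will provide a preliminary evaluation of clinical activity based on PSA response".

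**The concern.** The hypothesis has a direction: more expression, better response. The four classes carry an order that could show it. Fisher's exact test on a 2x4 table depends only on the counts in each class, not on which class is higher. It spreads its sensitivity over every kind of departure from equal response rates, including patterns that contradict the hypothesis.

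With 15 men there is little information to spare, and section 1.3.1 puts MMR deficiency and/or microsatellite instability at 1-3% of unselected prostate cancers. These analyses are the planned examination of the PD-1/PD-L1 part of the section 1.3.1 hypothesis and of a listed objective in section 2.3. A real gradient could be reported as no association because the test did not look for one.

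Two lesser points belong here. Percent PSA change is derived for every man but never related to the markers. And the undetectable-versus-progressive contrast leaves out every man whose outcome lies between the two.

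**Working it through.** **The plan's own figure.** The only sample-size figure is the Wilson interval table in section 11. It reproduces. For 6/15, with z=1.96 and p=0.4, the centre is (0.4 + 3.8415/30)/(1 + 3.8415/15) = 0.420 and the half-width is 1.96 x sqrt(0.24/15 + 3.8415/900)/(1 + 3.8415/15) = 0.222. That gives 19.8-64.3%, as printed. It concerns the PSA50 rate and says nothing about the biomarker tests.

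**Step 1: what Fisher can see.** The class sizes are illustrative: 4/4/4/3 men and 6 responders, so C(15,6) = 5005 equally likely allocations.

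- Rising pattern 0, 1, 2, 3 responders: C(4,0) x C(4,1) x C(4,2) x C(3,3) = 1 x 4 x 6 x 1 = 24 allocations.
- Scrambled pattern 2, 1, 0, 3: 6 x 4 x 1 x 1 = 24 allocations.

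Both tables have the same null probability and hence the same Fisher p. Tables at least as improbable total 369/5005 = 0.074.

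For the exact trend test, score the classes 0, 1, 2, 3. The expected total score is 6 x (0x4 + 1x4 + 2x4 + 3x3)/15 = 6 x 21/15 = 8.4. The two-sided p counts tables whose total is at least as far from 8.4 as the observed total.

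- Rising: total 1 + 4 + 9 = 14, distance 5.6; 37/5005 = 0.007. Doubling the one-sided tail instead, 2 x 31/5005, gives 0.012.
- Scrambled: total 1 + 0 + 9 = 10, distance 1.6; 2473/5005 = 0.49.

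A more skewed split, 7/3/3/2 with responders 1/1/2/2, gives Fisher 910/5005 = 0.18 and trend 161/5005 = 0.032.

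**Step 2: power under a gradient.** All inputs except n=15 are assumed. Marker and PSA change are bivariate normal with correlation rho, the test is two-sided 5%, and PSA50 is a cut at a 40% response rate. That rate is borrowed from the figure of about 40% that section 1.3.1 gives for advanced castrate-resistant disease. There were 10,000 runs. The last column relates class to percent PSA change instead of PSA50.

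| rho | class split (%) | Fisher | exact trend | gain, points | Spearman, PSA change |
|---|---|---|---|---|---|
| 0.3 | equal | 7.3% | 9.9% | 2.6 | 16.8% |
| 0.3 | 50/25/15/10 | 9.0% | 9.5% | 0.5 | 14.9% |
| 0.4 | equal | 11.0% | 15.3% | 4.3 | 27.1% |
| 0.4 | 50/25/15/10 | 12.4% | 14.5% | 2.1 | 24.0% |
| 0.5 | equal | 15.7% | 23.6% | 7.9 | 40.6% |
| 0.5 | 50/25/15/10 | 19.1% | 23.2% | 4.1 | 37.2% |
| 0.7 | equal | 34.9% | 50.5% | 15.6 | 76.8% |
| 0.7 | 50/25/15/10 | 39.8% | 48.6% | 8.8 | 71.6% |

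At a 53% PSA50 rate, rho 0.7 and equal classes, Fisher 36.8% rises to trend 54.0%, a gain of 17.2 points. Part of Fisher's deficit is conservatism: it rejects about 2-4% of the time under the null.

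**Step 3: does the further gain from percent PSA change hold up?** Under the same model at 40% response, the planned CD4/CD8 t-test against Spearman on PSA change is 13.8% versus 17.6% at rho 0.3, 31.6% versus 43.8% at 0.5, and 63.4% versus 81.0% at 0.7.

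Now assume instead that the marker is shifted by 1.2, 1.5 or 1.8 SD in responders and is unrelated to PSA change within responders and within non-responders. The t-test has about 54%, 75% and 87%; Spearman has about 39%, 51% and 65%. The order reverses. Trend still beats Fisher under this model: across both models, for rho 0.6-0.7 or shifts of 1.2-1.8 SD, the gain is about 7-21 points.

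**Step 4: when trend loses.** If response depends only on below 1% versus the rest, the three upper classes share one response rate and the linear scores are wrong. Trend then loses a few to about 12 points to Fisher, and somewhat more in the extreme case where no man below 1% responds.

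**The case against.** The strongest reply is that the planned outcome matches the stated objective. Section 2.3 and the synopsis ask about association with PSA50 response, so making percent PSA change the main outcome would change the question. That stands, and PSA50 should stay.

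A reader might infer that cutting PSA change to yes/no costs this trial a fixed, large amount of power in both the PD-1/PD-L1 and the CD4/CD8 tests. The documents do not support that. They give no correlation, class distribution or alpha, and step 3 shows the sign reversing for CD4/CD8 under a plausible alternative. That alternative is not far-fetched. Section 3.3 sets no limit on PSA doubling time, and section 1.1.2 says natural history varies widely, so PSA rise in non-responders may reflect untreated growth unrelated to the marker.

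It can also be said that section 1.3.1 speaks of positive expression, which may mean positive versus negative and not a gradient. This stands in part. It is the case in which trend loses to Fisher, but a four-class Fisher test is not aimed at that question either.

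The undetectable-versus-progressive contrast is additional to the responder comparison and names no test. It is not a replacement for the all-patient analysis, so the complaint about it is limited to how it is read.

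Finally, these analyses are exploratory, paired with descriptive statistics, and carry no decision rule. That stands and sets the severity.

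**Conclusion.** The plan records an ordered marker and then uses a test that discards the order. The tables in step 1 show this without assuming any correlation; they rest only on illustrative class sizes.

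The size of the gain does rest on assumptions. With a 40-53% PSA50 rate, two-sided 5% and a bivariate-normal model, moving from Fisher to the exact trend test recovers about 4-17 points at rho 0.5-0.7 and roughly 0.5-3 points at rho 0.3. The further gain from percent PSA change is large only if the marker tracks PSA change within responders and within non-responders. If it does not, the planned CD4/CD8 t-test is the stronger test.

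Fisher's test remains valid here, and neither test makes 15 men adequate: at rho 0.5 the trend test reaches only about 23% in the cases tabulated. Low severity. It is an efficiency improvement to exploratory analyses and touches no primary or secondary result and no stated figure.

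**What to change.** In section 11.1.3.1 and the synopsis:

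1. Keep PSA50 as the outcome. Replace Fisher's test for PD-1 and PD-L1 with an exact Cochran-Armitage trend test across the four recorded classes. State the scores (0, 1, 2, 3) and the two-sided definition. Keep the cross-tables as description.
2. Beside the planned tests, not in place of them, add a supportive Spearman correlation in all men between each marker and the percent PSA change already derived for section 9.3.1. Use PD-1 and PD-L1 class, and CD4+, CD8+ and FOXP3+ density. Name in advance which of the two PSA summaries is used.
3. Label the undetectable-versus-progressive contrast as descriptive, because it leaves out the men in between.

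The cost is a few sentences and a few lines of code, with no new data, samples or patients. The trend test assumes a monotone relation; if the sponsor in fact expects only a positive-versus-negative effect, the plan should say so before the correlatives are analysed. Percent PSA change is not a confirmed response, and men with undetectable PSA are close to tied at the -100% floor, which is a further reason to keep that analysis supportive.
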